All information concerning the study device supplied by Fundación Investigación HM Hospitales in connection with this study, and not previously published, is considered confidential and proprietary information. This information includes the clinical investigation plan, subject informed consent and case report forms. This confidential information shall remain the sole property of Fundación Investigación HM Hospitales, shall not be disclosed to others without prior written consent from Fundación Investigación HM Hospitales and shall not be used except in the performance of this study.

The information developed during the conduct of this clinical study is also considered confidential and will be used by Fundación Investigación HM Hospitales in connection with the development of the study device. This information may be disclosed as deemed necessary by Fundación Investigación HM Hospitales.

The below-named individuals are authorized to sign this clinical investigation plan and its amendments.

_____ / _____ / _____

Signature

Date

Printed Name

Title

1. - SUMMARY

1. Study Title:	Epidural Pulsed Radiofrequency versus Epidural Steroids Injection for Treatment of Failed Back Syndrome: A Prospective, Randomized, Single-Blind and Multicenter Study
2. Sponsor:	Fundación Investigación HM Hospitales
3. Type of Clinical Investigation:	Clinical Investigation with CE-marked medical devices.
4. Coordinating Investigator:	[name] [name], MD PhD.
5. Protocol Code:	EPIPUL
6. Geography	Spain
7. Clinical Sites:	
Hospital Universitario Puerta de Hierro (Madrid, Spain).Hospital Universitario Rey Juan Carlos (Madrid, Spain).Hospital Universitario de Sanchinarro (Madrid, Spain)Hospital Fremain Majadahonda (Madrid, Spain)Hospital Universitario La Fé (Valencia, Spain)Hospital Clínico Universitario de Santiago (Santiago de Compostela, Spain)
8. Study Purpose:	The present pilot study suggests that the epidural application of PRF to the dorsal roots and proximal DRG can be safe and effective in the treatment of intractable pain after back surgery. Several explanatory hypotheses motivate further study of this apparent improvement over transforaminal PRF, which has produced inconsistent results in published reports to date.
9. Treatments	Experimental Group (62 patients): Epidural radiofrequency by catheter in the epidural space plus steroids administration. Control Group (62 patients): Epidural steroids injection.

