	
Inclusion Criteria:
 
1. Men and women over 18 years old.2. Written informed consent according to ICH/GCP and Spanish legislation, obtained before any study procedure.3. Pain VAS score at least 5 points.4. Duration of pain at least 3 months after back surgery with conservative treatment.5. Leg-dominant radicular pain deemed neuropathic based on clinical history and examination.6. Responsive to selective radicular nerve block (bupivacaine 0.125%).7. Patients who have had a previous epidural steroid injection. 
Exclusion Criteria:
 
1. Pregnancy or lactation.2. Inability to give informed consent in the absence of a legal representative.3. Subjects that are participating in a study with medicines or other clinical devices.4. Those who show inability to follow the instructions or collaborate during the development of the study.5. If in the opinion of the researcher there are findings in the physical examination, abnormalities in the results of the clinical analyses or other medical, social or psychosocial factors that could have a negative influence.6. Patients with myelopathy, systemic diseases, infection (systemic or local), cancer, indication for immediate surgery, coagulation disorders, use of anticoagulants, diabetes mellitus or multiple sclerosis.7. Life expectancy of less than one year.8. A current diagnosis of a progressive neurological disease.
14. Study Population:	Patients with chronic lumbar radicular pain following failed back surgery.
15. Sample Size:	62 patients per group, a total of 124 patients.
16. Research Ethics Committee:	CEIm HM Hospitales
17. Calendar:	
The total duration of the study from first enrolment to last subject last visit is estimated to be 28 months:
 
• 4 months to prepare all documentation for contracts and Committee approval.• 12 months for enrolment.• 6 months follow up.• 6 months to close the investigation and provide final study report.

2. – INDEX

1. - SUMMARY	3
2. – INDEX	5
3. - GENERAL INFORMATION.....	7
3.1 Clinical Investigation Identification	7
3.2 Type of Study.....	7
3.3 Description of the Device Study.....	7
3.4 Data Related to the Sponsor	7
3.5 Monitor Identification	7
3.6 Information on the Investigator Team	7
3.7 Expected Duration of the Clinical Investigation	7
3.8 Data Safety Monitoring Board (DSMB)	8
4. - JUSTIFICATION.....	8
5. - HYPOTHESIS AND ENDPOINTS	10
5.1 Hypothesis.....	10

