7.1 Type of Clinical Investigation

Prospective, randomized, single-blind and multi-center study.

Controlled comparison between epidural and transforaminal electrode placement and epidural steroids injection.

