7.2 Randomization Process

The clinical investigation will be single-blind. The assignment to the type of surgical treatment is carried out randomly and open for the investigators but not for

the patients. Randomization will be done with concealment of the randomization sequence and it takes place after informed consent has been signed.

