The electrode will be connected to an output of the RF generator (Cosman RFG-4-120V/GF RF Generator). To provide a monopolar PRF operation, a ground pad (Cosman DGP-PM-10) will be placed on a shaved muscle part of the posterolateral thigh skin and connected to the reference socket of the RF generator with voltage 0 for 240 seconds (to ensure single-blind).

Intravascular and subdural placement will be ruled out by injecting 1-1.5 ml of non-ionic radiographic contrast (180 mg of iohexol per ml) through the integral injection port of the electrode under live fluoroscopy. Subsequently, betamethasone 12 mg will be administered.

After treatment, the needle and electrode will be removed. A sterile dressing will be applied over the needle insertion site. The patient will be monitored (visualized by fluoroscopy) while the sedation is removed, the motor dysfunction of the leg is verified and then the patient will be discharged.

9.2 Experimental Group. Epidural Pulsed Radiofrequency.

A radiopaque, guidable radiofrequency electrode (Cosman RCE-E401519-P) will bend slightly at a 45° angle proximal to its metal tip and then be inserted through the needle. The electrode shall include an active 20/15 mm gauge tip, a 19/40 cm gauge shaft, a rounded distal point temperature sensor, an injection port and an integral generator connection. The electrode will be visualized by fluoroscopy as it is guided in the epidural space from the sacral canal to the lumbar vertebral canal. The electrode will be connected to an output of the RF generator (Cosman RFG-4-120V/GF RF Generator). To provide a monopolar PRF operation, a ground pad (Cosman DGP-PM-10) will be placed on a shaved muscle part of the posterolateral thigh skin and connected to the reference socket of the RF generator.

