The active tip of 15 mm of the electrode will be placed in the internal aspect of the pedicle in each of levels L4, L5 and / or S1, on the right or left side, according to the patient's pain distribution (Figure 1). Intravascular and subdural placement will be ruled out by injecting 1-1.5 ml of non-ionic radiographic contrast (180 mg of iohexol per ml) through the integral injection port of the electrode under live fluoroscopy. At each treated level, motor stimulation (50 Hz, 1 ms) of less than 0.4 volts will reproduce the patient's pain and motor stimulation (2 Hz, 1 ms) of less than 0.6 volts will result in a contraction muscle in the leg. The pulsed radiofrequency will be applied for 240 seconds (4 minutes), where the pulses of 45 volts and 20 milliseconds (ms) will be administered at 2 Hz (pulses per second) and the pulse width will be regulated to maintain the temperature at 42 °C or less. (E-dose = Vary Width). The steady-state impedance and current will be measured for each PRF epidural treatment at L5 and S1 levels using the 20-gauge, 15 mm active tip.

After the experimental treatment, the needle and electrode will be removed without injecting or any other substance capable of producing pain relief. A sterile dressing will be applied over the needle insertion site. The patient will be monitored while the sedation is removed, the motor dysfunction of the leg is verified and then the patient will be discharged.

10. - PRACTICAL CONSIDERATIONS AND ETHICAL ASPECTS

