11.1 Insurance Policy

According with current clinical trial legislation, this clinical trial does not require an insurance policy since the devices under study are used under the authorized conditions of use and the study does not imply an increase in the risk to the patient.

12. - PUBLICATIONS RIGHTS

Principal Investigator shall have the right to publish the results of the Study in any abstract, paper, presentation or manuscripts (not limited enumeration).

Principal Investigator shall give BOSTON SCIENTIFIC a reasonable period of 30 (thirty days) to review and comment upon an intended publication of Principal Investigator regarding the results of the Study prior to publication, to determine if any Intellectual Property Rights and/or Confidential Information should be removed. BOSTON SCIENTIFIC shall respond promptly in writing to Principal Investigator with any comments or objections, setting forth such information in reasonably sufficient detail.

Principal Investigator shall consider BOSTON'S SCIENTIFIC comments and/or objections in good faith and shall cause any and all appropriate changes to be made prior to further distribution and publication.

13. - STATISTIC ANALYSIS

A descriptive analysis of the categorical variables was performed using absolute and determined frequencies; and in the numerical variables, through the mean and

standard or median deviation and 25th and 75th percentiles, according to compliance with the assumption of normality.

The analysis of the main variable, pain difference between baseline measurement and 6 months after treatment in the radiofrequency group plus steroids vs steroids, will be carried out using a contrast of means with the t-Student or U Mann-Whitney test in case of not being able to fulfill the corresponding assumptions.

The size of the effect is estimated with Cohen's letter, interpreting a Cohen's letter <0.01 as "very small", between 0.01 to 0.2 as a "small" effect, around 0.5 an "average" effect ", from 0.8 to infinity, a" large "effect, according to the categorization of Cohen and Sawilowsky (Cohen, Jacob (1988). Statistical analysis of power for behavioral sciences. Routledge; Sawilowsky, S (2009). "New effect size rules of thumb". Journal of Modern Applied Statistical Methods. 8 (2): 467–474.).

If the imbalance is observed between the two groups, linear regression will be executed to adjust for variables that are observed unbalanced between them.

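### Six centres recruit, but no balancing by centre is specified and centre could enter the analysis only through a threshold-free, after-the-fact rule; stratifying and adjusting is a cheap gain in precision and pre-specification

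*Combined protocol and SAP*

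**What the plan says.** Section 7.1 describes a "Prospective, randomized, single-blind and multi-center study", and item 7 of the summary lists six hospitals, four of them in or near Madrid, one in Valencia and one in Santiago de Compostela. Item 15 of the summary sets "62 patients per group, a total of 124 patients".

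Section 7.2 is the whole allocation plan. Assignment is "carried out randomly and open for the investigators but not for" the patients, and "Randomization will be done with concealment of the randomization sequence and it takes place after informed consent has been signed". It does not mention how the sequence is generated, blocks, strata, minimisation or any role for centre.

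Section 13 makes the primary comparison a two-sample t-test on the change in VAS from baseline to 6 months, with a Mann-Whitney test if the assumptions fail. Covariates come in by one route: "If the imbalance is observed between the two groups, linear regression will be executed to adjust for variables that are observed unbalanced between them". No variables are listed and no criterion for imbalance is given. Centre and operator are not mentioned.

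In both arms (sections 9.1 and 9.2), "The electrode will be visualized by fluoroscopy as it is guided in the epidural space from the sacral canal to the lumbar vertebral canal". In the experimental arm the active tip is then placed "in each of levels L4, L5 and / or S1, on the right or left side, according to the patient's pain distribution".

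**The concern.** Pain at 6 months may differ between hospitals. Case mix, local pain management and the judgement that a patient responds to the nerve block (inclusion criterion 6, with no stated cut-off) can all vary, and the procedure is guided by hand. If allocation is not balanced within centres, some centres will by chance contribute more to one arm than the other. A test that ignores centre then carries the differences between hospitals as noise.

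The rule in section 13 is a weak safeguard. It rarely reaches centre (see the check below). Because it has no threshold and no variable list, whoever runs the analysis can decide after seeing the data whether centre, or anything else, is in the model. At stake are some precision and a primary result that does not depend on a choice made late.

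**Working it through.** **Inputs from the documents (section 7.3).** Two-sided alpha 0.05, power 90%, means 40 and 60 mm (difference 20 mm), SD 30 mm in both arms, losses 20%, 62 per arm. Six centres (summary, item 7).

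**Inputs assumed, because the documents give none.** ICC by centre 0.02 to 0.10. Near-equal centres: 124/6 = 20.7, taken as 21, 21, 21, 21, 20, 20. Losses unrelated to centre.

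**1. The plan's own figure.** The two-sample t-test (noncentral t) needs 48.26, so 49 per arm. Then 49/(1 − 0.20) = 61.25, rounded up to 62. The stated sample size reproduces.

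**2. Precision without centre.** SE = 30 × √(2/49) = 6.06 mm. Power by normal approximation is Φ(20/6.06 − 1.96) = Φ(1.34) = 91.0%.

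**3. Precision with balanced allocation and centre in the model.** Centre variance is taken as part of the 30 mm SD, so residual SD = 30 × √(1 − ICC).

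| Assumed ICC | Residual SD (mm) | SE (mm) | 20/SE − 1.96 | Power |
|---|---|---|---|---|
| none removed | 30.0 | 6.06 | 1.34 | 91.0% |
| 0.02 | 29.7 | 6.00 | 1.37 | 91.5% |
| 0.05 | 29.2 | 5.91 | 1.43 | 92.3% |
| 0.10 | 28.5 | 5.75 | 1.52 | 93.6% |

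The SE falls by about 1% to 5%. With the noncentral t, which charges for the five degrees of freedom (91 instead of 96), the powers are 90.4% without centre and 91.0% to 93.1% with it, so the gain is about the same.

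**4. How uneven centres would be if allocation ignored centre.** With 62:62 fixed overall and the centre sizes above, random permutation puts at least one centre at 65:35 or worse in about 65% of trials. With permuted blocks of 4 within centre, none reached 65:35.

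**5. What the conditional rule would do.** The plan sets no threshold, so take a chi-square test of centre by arm at p < 0.05 as an example. Under random allocation it flags imbalance in about 5% of trials. Centre would therefore almost never enter the model by this route.

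**6. Validity.** In simulation (1,500 runs per scenario, ICC 0.05 to 0.20), the unadjusted estimate averaged about 20 mm when the true difference was 20 mm. Type I error without stratification was 4.5% to 6.3%, which is 5% within simulation error.

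**7. Both halves are needed.** At ICC 0.05 with equal centres and allocation ignoring centre, adjusting for centre gave 89.7% power against 90.7% unadjusted, which is no gain within a Monte Carlo error of about 0.7 points. With blocks within centre plus adjustment it was 91.7%. At ICC 0.10 the stratified, adjusted figure was 92.9%, against 91.3% unstratified and unadjusted.

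**The case against.** The strongest reply is that this is a reporting gap plus a small efficiency point. Much of that stands.

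- **Silence is not a design.** A reader might infer that the sequence is unrestricted, is not balanced by centre, and so cannot deliver 62 per arm. Section 7.2 says none of this. The stated 62 per group is at least as consistent with some form of restriction. What can be said is that no balancing is specified.
- **There is no bias.** A reader might infer that differences between hospitals distort the arm comparison. Randomisation keeps the unadjusted test valid, and its standard error already covers chance imbalance. Centre variance lies inside the 30 mm SD and is not an extra error on top of it.
- **Uneven centres are not useless centres.** A reader might infer that a lopsided centre allows no comparison. A 7:13 split keeps 4 × 7 × 13/400 = 91% of balanced efficiency. Even under unrestricted allocation, a centre of 20 splits 4:16 or worse with probability only 0.012.
- **Operator freedom is limited.** Section 9.2 gives the anatomical target, contrast check, stimulation thresholds, pulse settings and a temperature ceiling, and the levels follow the patient's pain. Catheter insertion is common to both arms.

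What the reply does not answer is the analysis rule. Section 13 actively states an unadjusted test followed by regression on whatever looks unbalanced. That is a choice of model after the data are seen, and supplying a missing detail elsewhere does not cure it.

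**Conclusion.** The point holds as a low-cost improvement of modest size. Balancing by centre and always adjusting for it would bring power from about 91.0% to between 91.5% and 93.6%, and the standard error from 6.06 mm to between 6.00 and 5.75 mm, with the same 124 patients. This rests on an assumed ICC of 0.02 to 0.10, near-equal centres and 49 completers per arm; a smaller ICC would leave almost nothing to gain. The benefit that does not depend on the ICC is a primary model fixed in advance.

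The sample size stands, and nothing here invalidates the planned test. Stratification also has a limit. If operators differ in how they deliver radiofrequency, that affects one arm only and would appear as a treatment-by-centre interaction, which neither stratification nor a centre term removes.

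**What to change.** **Section 7.2.** State that patients are randomised 1:1, stratified by centre, in permuted blocks of randomly varying size, with the list held centrally and block sizes concealed from the sites. Varying sizes matter because investigators see each allocation and could guess the next one in a small fixed block.

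**Section 13.** Make the primary analysis a linear model of the change in VAS at 6 months with treatment, and with centre as a fixed factor in all cases. State in advance how very small centres are pooled. This model replaces the t-test or Mann-Whitney test as primary, since neither takes a centre term; keep them as a sensitivity analysis. Delete observed imbalance as a route to choosing the primary model, for every variable and not only for centre. Tabulate the arm difference by centre, descriptively. Recording the operator in the CRF would help in reading that table.

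**Cost.** A rewritten primary-analysis paragraph, a sentence or two in section 7.2, a stratified list, and about five degrees of freedom. No more patients are needed. Stratification cannot be added retrospectively, so it should be settled before enrolment; the change to section 13 can still be made until allocation-linked outcome data are examined.

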7.3 Sample Size and justification

Pain reduction at least thirty millimeters between the baseline visit and the 6 months visit in patients assigned to the experimental group evaluated by the Visual Analogue Scale (VAS). Pain reduction of twenty millimeters less in the experimental group than in the control group since the baseline visit and the 6 months visit evaluated by the Visual Analogue Scale (VAS).

To achieve a power of 90.00% to detect differences in the contrast of the null hypothesis $H_0: \mu_1 = \mu_2$ through a bilateral T-Student Test for two independent samples, taking into account that the level of significance is 5%, and assuming that the mean of the difference in VAS of the 6-month radiofrequency plus steroid group is 40 mm, the average of the control group is 60 mm and the standard deviation of both groups is 30 mm, with an estimate of losses of the 20%, it will be necessary to include 62 patients per group, total of 124 patients.

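### Section 7.3 states the planned effect in the wrong direction and does not say whether 40, 60 and 30 mm are changes from baseline or 6-month scores

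*Combined protocol and SAP*

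**What the plan says.** Section 7.3 opens with two statements about the expected effect. The first, for the experimental arm, is "Pain reduction at least thirty millimeters between the baseline visit and the 6 months visit". The second compares the arms: "Pain reduction of twenty millimeters less in the experimental group than in the control group".

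The sample-size sentence then assumes that "the mean of the difference in VAS of the 6-month radiofrequency plus steroid group is 40 mm", that "the average of the control group is 60 mm" and that "the standard deviation of both groups is 30 mm". The test is a two-sided two-sample t-test at 5% with 90% power. Allowing for 20% losses, this gives 62 patients per group, 124 in total.

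Section 5.1 sets out to show pain reduction with epidural pulsed radiofrequency against epidural steroids. Section 5.2 defines the primary endpoint as the between-group difference in pain reduction from baseline to 6 months. Section 13 takes as its main variable the "pain difference between baseline measurement and 6 months after treatment" and compares means by t-test, or by Mann-Whitney if assumptions fail. Linear regression adjustment is added only if imbalance between the groups is seen.

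**The concern.** The planned effect should point the same way as the hypothesis, and the SD in the power calculation should be that of the variable tested. Section 7.3 does not achieve both on any one reading.

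Taken literally, the experimental arm improves by 40 mm and control by 60 mm. The comparative sentence says the same thing, so this is more than one slipped word. A reader who takes the section at face value would conclude that the trial was planned around an advantage for control.

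The natural repair is to treat 40 and 60 mm as pain scores at 6 months. That restores the direction, but then 30 mm describes the spread of a score and not of the change that Section 13 tests. The two SDs can differ appreciably, and the documents give no source for the 30 mm, no baseline SD and no baseline-to-6-month correlation.

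**Working it through.** **1. Reproducing the plan's figure.** Inputs from Section 7.3: difference |40 − 60| = 20 mm, SD 30 mm, two-sided 5%, power 90%, losses 20%.
- Standardised difference: 20/30 = 0.667.
- Two-sample t-test (noncentral t): n = 48.26, so 49 per arm.
- Losses: 49/(1 − 0.20) = 61.25, so 62 per arm and 124 in total, as stated.
- Power at 49 evaluable per arm: 90.4%.

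Replacing +20 by −20 changes none of these numbers.

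**2. The two readings side by side.**

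| | 40 and 60 mm are changes | 40 and 60 mm are 6-month scores |
|---|---|---|
| Label (a difference in VAS) | fits | does not fit |
| Reduction of at least 30 mm, experimental | fits (40 ≥ 30) | fits if baseline is about 70 (70 − 40 = 30) |
| Reduction 20 mm less than control | fits (60 − 40 = 20) | does not fit (30 against 70 − 60 = 10 is 20 mm more) |
| Hypothesis in 5.1 | contradicted | fits |
| SD matches the variable in Section 13 | yes, if 30 mm is the SD of change | no |

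The baseline of 70 mm is an assumption; no section gives an expected baseline.

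**3. Change-score power if 30 mm is a 6-month SD.** With baseline SD s₀ and correlation r, both assumptions,

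SD of change = √(30² + s₀² − 2·r·30·s₀).

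Power to detect 20 mm with 49 evaluable per arm:

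| s₀ (mm) | r | SD of change (mm) | Power |
|---|---|---|---|
| 30 | 0 | 42.4 | 64% |
| 30 | 0.3 | 35.5 | 79% |
| 30 | 0.5 | 30.0 | 90% |
| 30 | 0.7 | 23.2 | 99% |
| 14.4 | 0 | 33.3 | 84% |
| 14.4 | 0.3 | 29.1 | 92% |

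The 14.4 mm is the SD of a uniform distribution from 50 to 100 mm (50/√12). It illustrates an entry floor of 5 points, taken as 50 mm on a 100 mm scale.

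The SD of change equals 30 mm when r = s₀/60, that is, at r = 0.5 for s₀ = 30 and about 0.24 for s₀ = 14.4. Below that value power is under the stated level; above it, power is higher.

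**4. Baseline-adjusted comparison of 6-month VAS.** The regression slope on baseline minimises the residual variance of (6-month VAS − b × baseline VAS). A slope of b = 0 is the 6-month score and b = 1 is the change. The adjusted SD therefore cannot exceed either one.
- If 30 mm is the SD of change, the adjusted SD is at most 30 mm.
- If 30 mm is the 6-month SD, the adjusted SD is 30·√(1 − r²): 30.0 mm at r = 0 (90.4%), 28.6 mm at r = 0.3 (92.8%) and 26.0 mm at r = 0.5 (96.5%).

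Estimating the slope costs one degree of freedom. Allowing for that and for chance baseline imbalance lowers the r = 0 figure only to about 90.1%.

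**The case against.** The strongest reply is that nothing in the calculation is wrong. The sample size reproduces exactly, the test is two-sided, and the figures are labelled a difference in VAS. On that label 30 mm is naturally the SD of change and matches Section 13. The direction is then a drafting or translation slip with no numerical effect. The arithmetic part of this stands in full.

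Three stronger inferences are tempting and are not supported.
- **That the stated 90% is not the power of the primary analysis, or that the trial is underpowered.** This needs 30 mm to be a 6-month SD, which is only an inference. Even then, power may be below, at or above 90%, and the documents do not say which. The reversed direction and the mismatched SD also belong to alternative readings of 40 and 60 mm, so they cannot both be charged at once.
- **That 30 mm contradicts 40 mm.** The text says at least thirty, and 40 satisfies that. Nor are 6-month scores the only reading that fits the figures; the literal change reading fits all three statements in 7.3 and fails only against 5.1.
- **That 30 mm and 20 mm are success criteria left untested.** They stand under the sample-size heading, and Section 13 tests only a difference in means.

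It can also be said that a t-test on change is valid under randomisation and that adjustment is a matter of taste. The first half is true. The second is not quite: adjustment uses a baseline VAS that is already collected, and it removes the dependence of power on which reading was meant.

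**Conclusion.** The defect is one of direction and definition, not of arithmetic. Section 7.3 states the planned effect against the hypothesis, in both the comparative sentence and the labelled means, and it does not define what 40, 60 and 30 mm measure. Neither reading reconciles 7.3 with both 5.1 and Section 13.

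The numerical consequence is conditional. If 30 mm is the SD of change, the 90.4% stands. If it is the SD of the 6-month score, change-score power spans 64% to 99% for correlations from 0 to 0.7 with an assumed equal baseline SD, and is 84% to 92% for correlations from 0 to 0.3 with an assumed baseline SD of 14.4 mm. The documents do not allow a choice within these ranges. The point should be corrected, but it is no reason to change the sample size.

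**What to change.** In Section 7.3:
- State that the expected mean reduction in VAS is 20 mm greater in the experimental group than in control.
- Say whether 40, 60 and 30 mm are changes from baseline or 6-month scores, and give the source of the SD. If 6-month scores are meant, say so: expected VAS of 40 mm (experimental) and 60 mm (control) at 6 months.
- Label 30 mm and 20 mm as planning values.

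In Section 13, make the primary analysis a comparison of 6-month VAS between arms adjusted for baseline VAS in all cases. This replaces the unadjusted t-test on change with adjustment only when imbalance is observed.

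The cost is a rewording of 7.3 and a short change in 13. No extra patients, visits or measurements are needed, since VAS is already collected at baseline and 6 months. Keep 62 per group, 124 in total.
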